#### 16.2.5. ANALYSIS OF OTHER SECONDARY EFFICACY ENDPOINTS

The distribution of subjects improved/the same/worsened from baseline in clinical status will be compared between treatment groups at Day 5 and Day 14 with a Mann-Whitney nonparametric test. The lowest observed value on the clinical status (NIAID) scale during between D1 to D5 and D1 to D14 will be used.

The number and percentage of subjects who have "improved", "same" or "worsened" based on their lowest NIAID ordinal scale between D1 to D5 and D1 to D14 will also be presented.

Document:	\[REDACTED]\net\enterprise\Apps\sasdata\SASb\SAS\Atea_Pharmaceuticals\AT-527\SZ\A63631\Biostatistics\Documentation\SAP\AT-03A-001_V1.0_COVID_SAP_PA7.doc		
Author:	\[REDACTED]	Version Number:	V1.0
		Version Date:	15Apr2021
Template No.:	CS_TP_BS016 Revision 6	Reference:	CS_WI_BS005

Effective Date: 02Dec2019

Copyright © 2009, 2010, 2012, 2016, 2018, 2019 \[REDACTED] All rights reserved. The contents of this document are confidential and proprietary to \[REDACTED] Holdings Inc. and its subsidiaries. Unauthorized use, disclosure or reproduction is strictly prohibited.

The proportion of subjects who died during the study regardless of the cause of death will be analyzed in the same manner as the primary efficacy endpoint at Day 10, 14, 28 and 63.

Kaplan-Meier curves (product-limit estimate) will be provided by treatment arm for the duration of hospitalization for COVID-19 (days), for the time to sustained non-detectable SARS-CoV-2 (days) and the time to first SARS-CoV-2 negative test (Days). Kaplan-Meier estimate of the time will be provided at the 25th, 50th (median), and 75th percentiles along with their corresponding two-sided 95% CIs. The estimates of the SEs will be computed using the Greenwood's formula, the CI for the median will be calculated according to Brookmeyer and Crowley (1982), and the CIs for the survival function estimates at each scheduled time point will be derived from the Kaplan-Meier estimates using the log-log transformation.

The p-value associated with the log-rank test statistic will be provided and compared at the two-sided 0.05 alpha level based on a null hypothesis that there is no difference between the two treatment groups and will be presented for descriptive purpose only. For the time to sustained non-detectable SARS-CoV-2 (days) and the time to first SARS-CoV-2 negative test (Days), separate analyses will be performed for:

- All subjects who have baseline quantitative SARS-CoV-2 above the limit of quantification.
- All subjects who have baseline quantitative SARS-CoV-2 above the median.
- All subjects who have baseline quantitative SARS-CoV-2 above  $4 \log_{10}$  copies/mL.
- All subjects who have baseline quantitative SARS-CoV-2 above  $6 \log_{10}$  copies/mL.

Number and proportion of subjects with SARS-CoV-2 positive will be provided by treatment group at each timepoint. The difference between the treatment groups will be presented with corresponding 95% CI. A Cochran-Mantel-Haenszel (CMH) general association test will be used to test for differences in rates between the treatment groups controlling for geographic region. Separate analyses will be performed for:

- All subjects who have baseline quantitative SARS-CoV-2 above the limit of quantification.
- All subjects who have baseline quantitative SARS-CoV-2 above the median.
- All subjects who have baseline quantitative SARS-CoV-2 above  $4 \log_{10}$  copies/mL.
- All subjects who have baseline quantitative SARS-CoV-2 above  $6 \log_{10}$  copies/mL.

Document: \net\enterprise\Apps\sasdata\SASt\SAStAtea\_Pharmaceuticals\AT

527\\$\\$ZA63631\Biostatistics\Documentation\SAP\AT-03A-001 V1.0 COVID SAP PA7.doc

**Author:**

### Version Number:

v1.0

Version Date:

15Apr2021

Template No : CS\_TP\_BS016 Revision 6

## Reference

CS WI BS005

Effective Date: 02Dec2019

### 16.2.6. OTHER SECONDARY ANALYSES

The following additional secondary analyses will be performed:

- The analysis of the time to clinical recovery by Day 14 (key secondary efficacy endpoint) will be repeated to analyze time to clinical recovery by Day 28 and 63. The data will be censored at Day 28 and Day 63 respectively instead of Day 14.
- The analysis of the proportion of subjects with RFD by Day 28 will be repeated to analyze proportion of subjects RFD by Day 10, 14, and 63, respectively.
- The secondary analysis of all-cause mortality will be repeated for deaths primarily due to respiratory failure and deaths due to other causes. The primary cause of death will be reported on the Death Details page of the eCRF.
- All-cause mortality at Day 10, 14, 28 and 63 will also be summarized by primary death cause using descriptive statistics.
- The observed NIAID scores and the change from baseline values will be summarized using descriptive statistics at each scheduled day. If a subject dies, the NIAID score of 6 will be carried forward to the later visits.
- The observed respiratory support levels and change from baseline values will be summarized using descriptive statistics at each scheduled day.

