6.9. Assessment of Study Subject Clinical Course

Assessment of study subject signs, symptoms and daily clinical course will be conducted regularly, as specified in [Table 6-1](#). These will include (and are not limited to):

- Daily recording of subjects' overall Clinical Status, from most severe to least severe, using a categorical scale similar to the ordinal scale of Clinical Status being used in the NIAID controlled trial design for comparatively assessing parallel study arms for treating COVID-19 patients (NCT04280705). From most severe disease to progressively less severe disease, the stages of this adapted ordinal scale of overall Clinical Status are defined as follows:

1. Death
2. Hospitalized, on invasive mechanical ventilation or ECMO
3. Hospitalized, on non-invasive ventilation or high flow oxygen devices
4. Hospitalized, requiring supplemental oxygen
5. Hospitalized, not requiring supplemental oxygen – requiring ongoing medical care (COVID-19 related or otherwise)
6. Hospitalized, not requiring supplemental oxygen – no longer requires close medical care for COVID-19

(Note: Examples include recovered subjects needing inpatient quarantining/confinement or needing social services connections for outpatient living.)

7. Not hospitalized, but with limitation on activities and needing close outpatient care for COVID-19 manifestations
8. Not hospitalized, no limitations on activities, no need for continued close medical care

Protocol Number: AT-03A-001

Subjects with Status 2 or 3 disease at Screening would not be eligible for the study, but enrolled subjects who progress to respiratory failure/mechanical ventilation during the study will have deteriorated to Status 2 on this scale. It is anticipated that most “moderate” COVID-19 patients eligible for this study will be enrolled with an overall Clinical Status of 4 or 5. During the study, subjects’ overall Clinical Status may worsen or improve. Maximal deteriorations will be to Status 1 (death). Deterioration to Status 2, corresponding to respiratory failure/mechanical ventilation, would require the subject to be discontinued from study treatment, and the subject would thereby be eligible for treatment with any therapies appropriate for severe COVID-19. Subjects will have achieved the secondary endpoint of “clinical recovery” with improvement to Status 6, 7 or 8.

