8.3.3. Other Secondary Analyses

The proportions of active-treated and placebo-treated subjects improving or worsening in their Clinical Status (NIAID scale) by at least one category will be indicated in tabular displays depicting end-of-treatment data (nominal Day 5) and primary study completion data (Day 14). Analyses (active vs. placebo) will compare the probabilities of ≥ 1 -category improvement and ≥ 1 -category worsening - for the treatment period (Days 1-5), and the primary study period (Days 1-14).

Other secondary analyses will be delineated in the SAP and will include comparative analyses (active vs. placebo) of various efficacy and safety parameters by descriptive statistics, comparisons of proportions, and/or time-to-event analyses as appropriate.

- Assessments of all-cause mortality will include sub-analyses of deaths primarily due to respiratory failure vs. deaths attributed primarily to other causes (e.g., co-morbidities, thrombo-embolic phenomena, etc).
- Longer-term outcome data (to Days 28 and 63) will be used to evaluate subjects' longer-term COVID-19 Clinical Status, using the NIAID scale.

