8.3.4. Handling of Missing Data

Patients with missing data due to death will be assigned the worst possible outcome, where applicable. Patients who do not complete D14 assessment and have study discontinuation for lack of efficacy, non-compliance with study drug, progressive disease, lost to follow-up, or adverse event will have primary endpoint response imputed as PRI. If study discontinuation reason was recovery, the primary endpoint will be imputed as no PRI. Other strategies for handling missing data will be described in the SAP.

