## 16.2. SECONDARY EFFICACY

### 16.2.1. KEY SECONDARY EFFICACY ENDPOINTS

#### 16.2.1.1. Change from Baseline in Quantitative SARS-CoV-2

The first key secondary endpoint is the change from baseline in amount of quantitative SARS-CoV-2 as measured by RT-PCR at the time points required in the protocol schedule of assessments (Days 2, 5, and 14). Quantitative SARS-CoV-2 will be assessed quantitatively via the TaqPath assay, and qualitatively via a separate assay, COBAS.

Analysis will be performed on the mITT analysis set only.

#### 16.2.1.2. Time to Clinical Recovery (days) by Day 14

The second key secondary endpoint is time to clinical recovery in days on or before Day 14, defined as

- Time to clinical recovery by Day 14 (days) = (Date of clinical recovery on or before Day 14 – Date of randomization) +1

Clinical recovery is defined as achieving the NIAID clinical status of level 6 or above, which include subjects who are no longer hospitalized (level 7 or 8) or hospitalized but not requiring supplemental oxygen (level 6). The clinical status and assessment date/time will be reported on the Ordinal Scale for Clinical Severity page of the eCRF.

The date of clinical recovery is based on the date the score is first  $\geq 6$ . Should there be no clinical recovery, then the time to clinical recovery is set to 15 days.

The 8 levels of NIAID are the following:

1. Death
2. Hospitalized, on invasive mechanical ventilation or ECMO
3. Hospitalized, on non-invasive ventilation or high flow oxygen devices
4. Hospitalized, requiring supplemental oxygen

Document: \\[REDACTED]\net\enterprise\Apps\sasdata\SASb\SAS\Atea\_Pharmaceuticals\AT-

527\SAZ63631\Biostatistics\Documentation\SAP\AT-03A-001\_V1.0\_COVID\_SAP\_PA7.doc

Author: [REDACTED]

Version Number: V1.0

Version Date: 15Apr2021

Template No.: CS\_TP\_BS016 Revision 6

Reference: CS\_WI\_BS005

Effective Date: 02Dec2019

Copyright © 2009, 2010, 2012, 2016, 2018, 2019 [REDACTED] All rights reserved. The contents of this document are confidential and proprietary to [REDACTED] Holdings Inc. and its subsidiaries. Unauthorized use, disclosure or reproduction is strictly prohibited.

5. Hospitalized, not requiring supplemental oxygen – requiring ongoing medical care (COVID-19 related or otherwise)
6. Hospitalized, not requiring supplemental oxygen – no longer requires close medical care for COVID-19  

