### 16.2.3. OTHER SECONDARY EFFICACY ENDPOINTS

#### 16.2.3.1. Proportion of Subjects Improving/Worsening from Baseline in Clinical Status Using the NIAID Ordinal Scale by Day 5 and 14

The endpoint is based on the lowest observed value on the clinical status (NIAID) scale between D1 to D5 and D1 to D14. Subjects will be classified as “improved”, “same” or “worsened compared to Baseline.

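### SAP 16.2.6 carries NIAID score 6 forward after a death, although death is 1 on that scale and 6 counts as clinical recovery

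*SAP*

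**What the plan says.** **Death code.** SAP 16.2.6 plans descriptive summaries of NIAID score and change from baseline at each scheduled day, with this rule: "If a subject dies, the NIAID score of 6 will be carried forward to the later visits".

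Protocol 6.9 and SAP 16.2.1.2 list the same eight-level NIAID scale, running from 1 (death) to 8 (best). Protocol 6.9 adds: "Maximal deteriorations will be to Status 1 (death"). SAP 16.2.1.2 states: "Clinical recovery is defined as achieving the NIAID clinical status of level 6 or above". The scale on which death is level 6 is the Respiratory Support scale (SAP 16.1.1).

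Protocol 8.3.4 says: "Patients with missing data due to death will be assigned the worst possible outcome, where applicable". Protocol 8.3.3 extends the NIAID scale to late follow-up: "Longer-term outcome data (to Days 28 and 63) will be used to evaluate" longer-term clinical status.

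**Improvement and worsening.** SAP 16.2.3.1 says: "The endpoint is based on the lowest observed value on the clinical status (NIAID) scale between D1 to D5 and D1 to D14". SAP 16.2.5 repeats this for a Mann-Whitney comparison of improved, same and worsened. Protocol 8.3.3 asks for the probability of improving by at least one category and the probability of worsening by at least one, over Days 1-5 and Days 1-14.

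**Later change.** The Changes to Planned Statistical Analyses Form of 16 March 2022 lists the improving/worsening analysis and all other secondary efficacy analysis as not presented. It says the SAP itself stays as it is.

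**The concern.** The rule enters a subject who has died at the level for someone still in hospital who needs neither oxygen nor close COVID-19 care. By the SAP's own definition that is a recovered patient. The likely cause is that the two ordinal scales were mixed up: they run in opposite directions, and 6 is the death code on the other one.

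The mean NIAID score and mean change would then be too favourable in any arm with deaths, from the first scheduled day after each death through late follow-up. If the arms had different numbers of deaths, the comparison between them would be distorted in favour of the arm with more.

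The second matter concerns the same scale. Low scores are severe, so the lowest score in a window is the worst status reached. That suits a count of worsening but is a poor basis for a count of improvement, which the protocol also asks for.

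**Working it through.** The plan states no figure that depends on either rule, so there is nothing to reproduce. The check compares definitions and then does simple arithmetic.

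**Inputs**
- Score assigned after death: 6 (SAP 16.2.6).
- NIAID score for death: 1 (Protocol 6.9, SAP 16.2.1.2).
- Baseline score expected for most subjects: 4 or 5 (Protocol 6.9).
- Arm size: 81 subjects randomized 1:1 in Part A (Protocol 3.2), so about 40 or 41 per arm. The interim analysis covered 70, about 35 per arm if evenly split.
- Deaths: no count is given, so results are per death.

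**Error for one subject.** 6 - 1 = 5 categories at every later visit.

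| Baseline | Change as coded | Change with death = 1 |
|---|---|---|
| 4 | 6 - 4 = +2 | 1 - 4 = -3 |
| 5 | 6 - 5 = +1 | 1 - 5 = -4 |

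The sign of that subject's change reverses.

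**Error in the arm mean.** Shift = 5 x deaths / subjects summarized. For one death:
- n = 40: 5/40 = 0.125
- n = 41: 5/41 = 0.122
- n = 35: 5/35 = 0.143

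With n = 40, a death from baseline 4 contributes +2/40 = +0.050 to the mean change instead of -3/40 = -0.075. From baseline 5 it contributes +1/40 = +0.025 instead of -4/40 = -0.100. The gap is 0.125 in both cases.

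**Direction against having no death.** Take one death and 39 survivors with mean score m (assumed values).
- m = 7.5: coded 6 gives (39 x 7.5 + 6)/40 = 7.4625; coded 1 gives (39 x 7.5 + 1)/40 = 7.3375. Both are below 7.5, so the death still lowers the mean, but by too little.
- m = 5: coded 6 gives (195 + 6)/40 = 5.025; coded 1 gives (195 + 1)/40 = 4.900. Here the death raises the mean above 5.

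The turning point is a survivor mean of 6. For change from baseline it is the dead subject's coded change, +2 or +1.

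**Lowest-score rule.** Table 6-1 (footnote a) puts the Day 1 ordinal assessment before the first dose, and SAP 6.2 takes the last pre-dose value as baseline. The Day 1 score is therefore normally the baseline. The SAP does not say whether it belongs to the D1-D5 and D1-D14 windows.
- If it does, the minimum cannot exceed baseline, and nobody can be improved unless the Day 1 score is missing or is not the baseline.
- If it does not, improved requires every recorded score to exceed baseline.

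To show how strict this is, list all courses with baseline 4 or 5 and four later scores from 1 to 8: 2 x 8^4 = 8,192. With the Day 1 score in the window, 0 are improved. Without it, 4^4 + 3^4 = 256 + 81 = 337 are. Those whose last score is above baseline number (4 + 3) x 8^3 = 3,584. These are counts of possible sequences, not probabilities.

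For example, baseline 5 followed by 5, 5, 6, 7 on Days 2-5 has minimum 5 and is classed as same, although Day 5 is 7 - 5 = 2 categories better.

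**The case against.** The strongest reply is that nothing delivered depends on either rule. The 16.2.6 summaries carry no test. Time to recovery, respiratory failure or death, and mortality each have their own derivation (SAP 16.2.1.2, 16.2.1.3, 16.2.3.2). The March 2022 form removes both affected outputs. This all stands, and it limits the weight of the point. It does not make 6 the right code, and the form does not correct it.

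A reader might infer that the arm with more deaths looks better at every later visit. The documents do not support that. Coding 6 makes the arm mean too high compared with coding 1, but the arm gains from a death only while its survivors average below 6. At Days 28 and 63 survivors may well average above that. The documents give neither the number nor the timing of deaths.

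A reader might also infer that deaths enter time to clinical recovery as recoveries. SAP 16.2.1.2 takes that endpoint from the clinical status recorded on the eCRF and assigns 15 days when there is no recovery. The sensitivity analysis in 16.2.4.2 censors deaths without recovery at Day 15. Nothing says the carried-forward value feeds it.

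On the lowest-score rule, Protocol 8.3.3 does not say whether best, worst or last status is meant, and SAP 3.3 logs a change to this analysis. A worst-status display is therefore allowable, and a Mann-Whitney test on three ordered categories is valid. The wording does not settle whether the pre-dose score counts. The laboratory section (SAP 17.3) specifies post-baseline values for D1-D14, while the clinical-status sections do not. What remains is that improvement is poorly captured on either reading.

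**Conclusion.** The death code is wrong as written, and no reading of the two documents makes 6 correct. Relative to correct coding, the mean NIAID score and mean change are too high by 5 x deaths / subjects summarized: 0.125 per death with 40 subjects, and 0.122 to 0.143 per death for arms of 41 down to 35. The effect is to understate harm from deaths. It can make an arm with more deaths look better, but only under the survivor condition shown in the working. The realised shift is unknown because no death count is given.

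The point is minor. It touches descriptive summaries that the changes form drops, and it alters no formal test, sample size or power statement.

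The lowest-score rule is a smaller issue. It serves worsening but does not measure the improvement that Protocol 8.3.3 also asks for. The size of the undercount cannot be computed from the documents.

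**What to change.** In the rule of SAP 16.2.6, carry forward NIAID score 1 after death. Because the SAP is not to be updated, record this on the changes form. The cost is one number.

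For SAP 16.2.3.1 and 16.2.5, state whether the pre-dose Day 1 score is in the window. Keep the lowest score for worsening. Define improvement separately, over the protocol's Days 1-5 and Days 1-14 periods, with death scored 1. The definition should say where a subject who both improves and worsens is placed. The Mann-Whitney test can stay. The cost is a revised definition and, if the table is ever produced, its reprogramming. No new data are needed.

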### 16.3. EXPLORATORY EFFICACY

The exploratory efficacy endpoints are:

- Time to a National Early Warning Score (NEWS) score  $\leq 2$  from Screening (days) for subjects whose Screening NEWS score was  $>4$  (the NEWS score is a subject triaging score developed in Europe);
- Time to COVID-19 symptom resolution;
- Individual COVID-19 symptoms severity over time;
- Level of C-Reactive Protein (CRP) over time (if data available);

Document: \net\enterprise\Apps\sasdata\SASt\SAStAtea\_Pharmaceuticals\AT-

527\\$\\$ZA63631\Biostatistics\Documentation\SAP\AT-03A-001\_V1.0\_COVID\_SAP\_PA7.doc

### Author:

### Version Number:

V1.0

Version Date:

15Apr2021

Template No.: CS TP BS016 Revision 6

## COVID-19 Statistical Analysis Plan

ATEA Pharmaceuticals  
Protocol AT-03A-001  
Page 42 of 77

- Level of IgG and IgM over time and change from baseline (if data available);
- Level of SARS-CoV-2 infectious virus titer (if data available);
- Serial assessment of the appearance of antibody to SARS-CoV-2 in study subjects' serum samples, when validated antibody tests become more widely available; (this endpoint will be covered in a separate SAP);
- Other relevant COVID-19-specific tests or SARS-CoV-2 tests that may become available (this endpoint will be covered in a separate SAP);
- Proportion of subjects with a  $\geq 1$ -tier increase PRI on or before Day 14;
- Time-weighted average change from baseline in quantitative SARS-CoV-2.

### 16.3.1. EXPLORATORY EFFICACY ENDPOINTS

### 16.3.1.1. Time to a NEWS Score $\leq 2$ (days)

An exploratory efficacy endpoint is the time to a NEWS score  $\leq 2$  from Screening, in days, for subjects whose screening NEWS score was  $> 4$ .

The NEWS identifies a subject at risk of deterioration and prompts critical care interventions. It is comprised of 7 physiological parameters. Each of these physiological parameters is rated using a 4-point Likert scale (0= no risk to 3 = high risk). The NEWS score is obtained by summing the 7 physiological parameter individual scores and ranges from 0 to 21, with higher score indicating higher risk of deterioration and need for escalation in clinical care, including transfer of the subject to a higher level of care hospital unit. The NEWS score is set to missing if at least one physiological parameter individual score is missing.

[figure not shown]
For subjects whose screening NEWS score was  $> 4$ , the time to a NEWS score  $\leq 2$  will be calculated as follows:

- Time to a NEWS score  $\leq 2$  (days) = (Earliest post-baseline assessment date where NEWS score is  $\leq 2$  – Date of the screening visit)

NEWS score data will be calculated using data from the Vital Signs page and the Level of Consciousness page of the eCRF collected on the same date. See details in [Appendix 5](#).

Missing baseline NEWS scores will be considered as  $\geq 4$ .

Document: \\[REDACTED]\net\enterprise\Apps\sasdata\SASB\SAS\Atea\_Pharmaceuticals\AT-527\ISZA63631\Biostatistics\Documentation\SAP\AT-03A-001\_V1.0\_COVID\_SAP\_PA7.doc  
Author: [REDACTED] Version Number: V1.0  
Template No.: CS\_TP\_BS016 Revision 6 Reference: CS\_WI\_BS005  
Effective Date: 02Dec2019 Version Date: 15Apr2021

Subjects with no post-baseline NEWS scores will be imputed at the first dose of study drug. Subjects who never met the criteria for NEWS scores  $\leq 2$  will have their time to NEWS score  $\leq 2$  imputed to one day after the maximum observed time to NEWS score  $\leq 2$ . If a subject dies, their time to NEWS score  $\leq 2$  will also be imputed to one day after the maximum observed time to NEWS score  $\leq 2$ .

Subjects will be censored as follows:

- If subject dies censor as 1 day after the largest observed time to achieving a NEWS score  $\leq 2$ .
- If subject has no post-baseline NEWS score, censor at Day 1.
- If no NEWS score  $\leq 2$  censor at the last non-missing NEWS score.

